## Study design and methods

The same protocol will be carried out in the two participating centres (Maggiore Hospital in Bologna and Molinette Hospital in Torino, Italy).

Participants will be patients recovering from a first episode of acute myocardial infarction or instable angina. Myocardial infarction will be documented by cardiac symptoms (presence of acute chest, epigastric, neck, jaw, or arm pain or discomfort or pressure without apparent non- cardiac source) and signs (acute congestive heart failure or cardiogenic shock in the absence of non-CHD causes) associated with ECG findings (characteristic evolutionary ST-T changes or new Q waves) and/or cardiac biomarkers (blood measures of myocardial necrosis, specifically CK, CK-MB, CK-MBm, or troponin, cTn). Instable angina will be documented by cardiac symptoms (chest pain lasting less than 20 minutes) with likely ECG findings (ST-segment depression and abnormal T-wave) in absence of myocardial necrosis biomarkers.

Medically eligible patients involved in the study have to meet, when screened 30 days after their index event, the following criteria: 1) a current diagnosis of at least one of the following: major or minor depression, dysthymia according to DSM-IV criteria, and demoralization according to DCPR criteria 2) no history of bipolar disorder (DSM-IV criteria), 3) no major depression with psychotic features, 4) no history of substance

abuse or dependency during the previous 12 months 5) no serious suicide risk 6) no current use of antidepressants 7) no current treatment with any form of psychotherapy 8) Mini-Mental State Examination score higher than 24; 9) written informed consent provided by the patient to participate. The patients' diagnoses will be established by the consensus of a psychiatrist and a clinical psychologist independently using the Structured Clinical Interview for DSM-IV (First et al, 1994). Patients who will meet all of the study's eligibility criteria will be administered, both at intake and at the end of the treatment, by the same clinical psychologist blind as to treatment assignment who had evaluated them on intake, both observer-rated (Paykel's Clinical Interview for Depression, CID, 1985) and self-rating questionnaires (Kellner's Symptom Questionnaire-SQ, 1987, and Ryff's Psychological Well-being Scales-PWB, 1989). Medically eligible patients with a prior episode of major depression will be enrolled if meeting the symptom criteria for a major or minor depressive episode for at least 7 rather than the usual 14 days. The DSM-IV duration criterion for dysthymia will not be changed.

After the initial assessment, patients will be randomized with a computer-generated program to 1 of 2 treatment groups: 1) cognitive behavioral treatment (CBT) combined with well-being therapy (WBT) according to a standardized protocol 2) standard clinical management (CM). In both groups treatment will consist of twelve, 45-minute sessions once a week and will be provided by 3 clinical psychologists, who will administer both types of interventions in the two groups. The usual format of CBT is one weekly therapy session coupled with daily practice exercises designed to help the patient apply CBT skills in their home environment. This approach involves several essential features: identifying and correcting inaccurate thoughts associated with depressed feelings (cognitive restructuring), helping patients to engage more often in enjoyable activities (behavioral activation), and enhancing problem-solving skills. The first of these components, cognitive restructuring, involves collaboration between the patient and the therapist to identify and modify habitual errors in thinking that are associated with depression. Depressed patients often experience distorted thoughts about themselves, their environment and their future. Information from the patient's current experience, past history, and future prospects is used to counter these distorted thoughts. In addition to self-critical thoughts, patients with depression typically cut back on activities that have the potential to be enjoyable to them, because they anticipate that such activities will not be worth their effort. Unfortunately, this usually results in a vicious cycle, where in depressed mood leads to less activity, which in turn results in further depressed mood, etc. The second component of CBT, behavioral activation, seeks to remedy this downward spiral by negotiating gradual increases in potentially rewarding activities with the patient. The aim of the therapy is also to make the patient aware of chronic and often subtle life stresses that exert harmful consequences on the individual over a certain amount of time. Examples may be unawareness of the longer time that an increasing age requires for recovering from demanding days, inadequate rest, prolonged anxiety, inappropriate sleeping habits, and inability to protect oneself from requests that exceed the potential of the individual. When patients are depressed, problems in daily living often seem insurmountable. In the final process, the CB therapist provides instruction and guidance in specific strategies for solving problems (e.g. breaking problems down into small steps). The techniques included in WBT that may be used in overcoming impairments in environmental mastery, purpose in life, personal growth, autonomy, self-acceptance and positive relations with others may

include: (a) cognitive restructuring (modification of automatic or irrational thoughts); (b) scheduling of activities (mastery, pleasure, and graded task assignments); (c) assertiveness training; (d) problem solving. CM will consist of reviewing the patients' clinical status, and providing the patient with support and advice if necessary. Specific interventions such as exposure strategies, diary work, and cognitive restructuring will not be allowed. The patient will be encouraged to share the main events that took place in the previous 2 weeks. Both CBT and CM intervention will be manualized. Treatment integrity will be checked by submitting 10 randomly selected sessions (5 involving CBT and 5 involving CM) to 2 independent assessors, who will have to rate the overall treatment integrity and identify all sessions. The treatment will be provided at Maggiore Hospital in Bologna, and at Molinette Hospital in Torino, in laboratory spaces expressly dedicated to the psychological interviews with the patients. The clinical psychologists involved in the study have to present substantial previous clinical experience with CBT and WBT, including treatment of depression also of patients with chronic disease or, more specifically, coronary disease.

The cardiologists involved in the study will evaluate the patients at intake and once every 6 months to monitor changes in clinical course of cardiac disease. Data from electrocardiogram, echocardiogram, X ray, blood pressure, blood samples (cholesterol levels, creatinine, glycosylated haemoglobin, C-reactive protein, coagulation/fibrinolysis biomarkers) and waist/hip ratio will be provided at intake. TIMI RISK SCORE for STEMI (Morrow et al, 2000) and GRACE RISK SCORE for UA/NSTEMI (Bassand et al, 2007) will also be detected at intake for mortality risk within 1 month after patients' cardiac index episode.

Both before and after psychological treatment, among laboratory testing, the following biomarkers will be investigated: urinary cortisol excretion, blood DHEA-S level, blood glycosylated haemoglobin, coagulation/fibrinolysis markers, urinary norepinephrine, urinary epinephrine. The association of these biomarkers with stress increases health risk, regardless of the presence of psychiatric disorder (Lupien et al, 1998). Among blood laboratory testing, hyperhomocysteinemias levels will be also detected, since elevated homocysteine metabolism was established as an independent risk for vascular disease (the risk increase directly with total homocysteine level 6% to 7% for every 1  $\mu$ mol/liter increase in total homocysteine level) (Folstein et al, 2007). Heart rate variability (HRV) will be also investigated. Decreased HRV, in fact, a predictor of mortality, is reduced in patients with major depressive disorder after ACS (Glassman et al, 2007). Moreover, markers of pathophysiological mechanisms implicated in ACS will be investigated since they provide incremental value over existing ischemic biomarkers. Systemic markers of inflammation such as elevated C-reactive protein (CRP) levels (Morrow et al, 1998) will be studied for its prognostic value (Biasucci et al, 1996).

Before and after psychological treatment, and then after 3, 6, 9, 12, 18 and 24 months the differences between the two groups in CID, SQ and PWB scores will be analyzed.

## STATISTICAL PLAN

The sample size was calculated based on the results of previous studies carried out by the Coordinator of the present project. According to the statistical analyses performed in previous studies focusing on treatment efficacy (Fava et al, 1998), a sample size of 100 patients (50 per treatment group) seems appropriate. In the present study, to obtain the

same difference between the mean CID scores with a power of 80%, at least 16 subjects per arm are required according to calculations performed with the piface software (Lenth, 2001, 2006-2009). Multivariate ANOVA will be used to examine differences in dimensional psychological variables (i.e. CID total score, SQ and PWB scales scores) between patients assigned to CBT-WBT and CM at pre-intervention. Mixed-model ANOVA (Repeated Measures) will be performed to test differences between groups (CBT-WBT or CM) on the CID total score, the PWB scales, and the SQ scale scores at different follow-up evaluations. For the comparison between the means of the two groups (CBT-WBT vs CM) in the scores of psychological measures (CID, SQ e PWB) and in the values of the biomarkers, analysis of the covariance will be used, considering baseline scores as covariates. The missing data will be analyzed with the Intention-To-Treat procedure. Survival analysis will be used in order to evaluate the period of time occurred between baseline and new negative cardiac outcomes. The follow-up time considered for relapse will be 24 months after the end of the treatment. Survival analysis will be used for time until relapse into cardiac events. Among factors investigated as possible predictors of outcome, assignment to CBT in combination with WBT or to CM will be included. The Kaplan-Meier method will be used for estimating survival curves. When relapse is the event of interest, survival will be referred to relapse-free status. The log-rank test and Cox proportional hazards model will be included to compare any survival distributions for each of the factors considered. For all tests performed, the significance level will be set at 0.05, two-tailed.

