*Endpoints.* As the primary end-point, the present research includes the improvement in depression as assessed by variations in overall CID score of at least 4.1 points, after CBT-WBT versus CM. The expected superiority of CBT-WBT versus CM is set to the 80%, at, if the pre/post treatment difference of CID scores is at least 4.1 points (Fava et al., 1998b). As secondary end-points the study includes: 1) the improvement of psychological distress and well-being evaluated through the variations in the overall Symptom Questionnaire (SQ) and Psychological Well-Being scales (PWB) scores; 2) the decrease of stress biomarker after CBT-WBT versus CM; 3) the reduction of cardiovascular major adverse events (cardiac mortality, recurrent heart attack and new hospitalization for cardiovascular causes) after CBT-WBT versus CM.

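### The repeated-measures model for CID, PWB and SQ at follow-up names no baseline covariate, and the plan does not say whether the baseline-adjusted ANCOVA covers those visits, so the long-term comparison may be less precise than the data allow

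*Combined protocol and SAP*

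**What the plan says.** The Statistical Plan gives two methods for the same three scales, in consecutive sentences.

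- **Repeated measures.** "Mixed-model ANOVA (Repeated Measures) will be performed to test differences between groups (CBT-WBT or CM) on the CID total score", with the PWB and SQ scales, at the follow-up evaluations. No covariate is named and none is excluded.
- **ANCOVA.** The sentence opens with its scope: "For the comparison between the means of the two groups (CBT-WBT vs CM) in the scores of psychological measures (CID, SQ e PWB"). It adds biomarker values to that scope and states that "analysis of the covariance will be used, considering baseline scores as covariates". No visit is named.

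The last paragraph of Study design and methods sets the occasions for CID, SQ and PWB: "Before and after psychological treatment, and then after 3, 6, 9, 12, 18 and 24 months". That is one pre-treatment and seven later assessments, listed as one series in which group differences are analysed.

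The primary endpoint, under Specific aims and preliminary findings, is depression improvement judged by "variations in overall CID score of at least 4.1 points, after CBT-WBT versus CM". SQ and PWB are secondary, with no stated effect size or power.

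**The concern.** Only the repeated-measures sentence is tied to the follow-up evaluations, and it has no baseline term. The ANCOVA sentence has one, but it groups the scales with biomarkers that are scheduled only before and after treatment. It can therefore be read as the end-of-treatment comparison alone, or as covering every visit.

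- If it is end of treatment only, the comparisons from 3 to 24 months are unadjusted, while the end-of-treatment comparison of the same scores is adjusted.
- If it covers every visit, the follow-up scores have two analyses, one adjusted and one not as written, and no rule says which decides.

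The eight-occasion list adds a second uncertainty. If the pre-treatment score is a level of the repeated factor, the group main effect averages in an occasion where randomisation makes the expected difference zero. The omnibus alternative is a group-by-time test on 7 degrees of freedom (8 occasions minus 1). The choice between main effect, interaction and ANCOVA would then be open after the data are seen.

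At stake is the width of the long-term intervals and the consistency of the reported comparisons. Bias is not at issue, because an unadjusted randomised comparison is valid.

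**Working it through.** **Inputs from the documents.** CID difference 4.1 points (Specific aims and preliminary findings); 80% power, at least 16 per arm, 50 per arm planned, and "the significance level will be set at 0.05, two-tailed" (all Statistical Plan).

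**Assumed, because the documents give no figure.** SD; correlation r between baseline and follow-up score (0.3, 0.5, 0.7); equal correlation between visits; complete data.

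**1. The plan's own figure.** With no SD stated, 16 per arm cannot be reproduced independently, only back-solved. A two-sided two-sample t-test with 16 per arm has 80% power at a standardised difference of 1.024, so SD = 4.1 / 1.024 ≈ 4.0. At SD 4.0 the t-test needs 16 per arm and the normal approximation 15. The figure is plausible but unverified.

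**2. Power for 4.1 points at 50 per arm, no adjustment.** SE = 4.0 × √(2/50) = 0.80. Then 4.1/0.80 − 1.96 = 3.165, giving power of 99.9%. At SD 5 it is 98.4% and at SD 6 it is 92.7%.

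**3. One visit.** Relative variance is 1 unadjusted and 1 − r² with ANCOVA. The detectable difference at 80% power is 2.80 × 0.80 × √(1 − r²).

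| r | Variance left | Reduction | Detectable CID difference (unadjusted 2.24) |
|---|---|---|---|
| 0.3 | 0.91 | 9% | 2.14 |
| 0.5 | 0.75 | 25% | 1.94 |
| 0.7 | 0.51 | 49% | 1.60 |

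At r = 0.5 the gain equals 1/0.75 = 1.33, or 33% more patients.

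**4. Mean of the seven post-baseline visits.** Unadjusted variance is (1 + 6r)/7; adjusted variance is that minus r².

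| r | Unadjusted | Adjusted | Ratio |
|---|---|---|---|
| 0.3 | 0.400 | 0.310 | 0.775 |
| 0.5 | 0.571 | 0.321 | 0.56 |
| 0.7 | 0.743 | 0.253 | 0.34 |

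These ratios depend on the correlation pattern. If correlation instead decays as 0.7 per 3 months (visits at 0, 3, 6, 9, 12, 15, 21 and 27 months), the reduction at the seven-visit mean is 19%, against 44% under equal correlation 0.5.

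**5. Baseline as a level.** With a constant effect δ, the group main effect over eight equally weighted occasions estimates (7/8)δ. Take equal correlation 0.5, 50 per arm and an assumed δ of 0.45 SD (normal approximation; noncentral F for group-by-time):

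- Baseline as a level: variance of the eight-occasion mean is (1 + 7 × 0.5)/8 = 0.5625, SE = √(0.04 × 0.5625) = 0.150, 0.394/0.150 = 2.63, power 75%.
- Group-by-time, 7 df: 55%.
- Seven follow-ups, unadjusted: SE = √(0.04 × 0.571) = 0.151, 0.45/0.151 = 2.98, power 85%.
- Seven follow-ups, baseline-adjusted: SE = √(0.04 × 0.321) = 0.113, 0.45/0.113 = 3.97, power 98%.

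At δ = 1.0 SD, close to what the plan's CID figures imply (4.1/4.0), all four exceed 99.9%. The differences in power therefore matter only for effects well below the planned CID effect.

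**The case against.** The strongest reply is that the plan already has the adjustment. The ANCOVA sentence covers the same three scales and the same group contrast and is not limited to one visit. Read with the sentence before it, it could describe one baseline-adjusted plan. This stands in part. A reader might infer that the plan makes no use of baseline scores for the follow-up comparison, and the documents do not support that: the repeated-measures sentence is silent on covariates, and the ANCOVA may reach the follow-up visits. But a separate ANCOVA does not put a baseline term in the model named for follow-up, and nothing says which of the two decides.

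Second, a reader might infer a substantial loss of power. The documents do not support that either. They give no SD and no correlation, the 0.45 SD effect is an assumption, and at the effect the plan's CID figures imply every option has power near 100%. This objection stands for CID at 4.1 points. It does not settle SQ and PWB, which have no stated effect, or late CID differences, since nothing says the 4.1-point difference lasts 24 months.

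Third, baseline as a level need not discard information: visit-specific or change-from-baseline contrasts can be drawn from such a model. That is correct, but the plan names no such contrast.

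Finally, the primary endpoint is CID improvement after treatment, where the adjusted ANCOVA is available on either reading. That stands and limits the point to the longer-term comparisons.

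**Conclusion.** The point holds as one of specification and precision. As written, the repeated-measures model has no baseline covariate, baseline may be one of its levels, and the scope of the ANCOVA at follow-up is not stated. The long-term CID, SQ and PWB comparisons may therefore be unadjusted and less precise than the collected data allow.

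For assumed baseline correlations of 0.3 to 0.7, the possible gain is a 9% to 49% cut in single-visit variance. The documents cannot narrow that range, and correlations with late visits may lie at its lower end. The benefit is narrower intervals, mainly for SQ, PWB and smaller late CID differences. The primary end-of-treatment comparison and the validity of the randomised comparison are not in question. The change is worth making because the plan already accepts this adjustment for these scales and the baseline scores are already collected.

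**What to change.** Rewrite the repeated-measures sentence. The outcomes are the end-of-treatment, 3, 6, 9, 12, 18 and 24-month scores of each scale. The model terms are baseline score, baseline-by-visit, treatment, visit and treatment-by-visit. The group difference at each visit is read from that model, so that the end-of-treatment and follow-up comparisons carry the same adjustment. The pre-treatment score is then a covariate and not an outcome level, and the question of which analysis decides at follow-up is closed.

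The cost is one sentence and a few degrees of freedom, with no new data. ANCOVA can stay for the biomarkers, which are scheduled only before and after treatment.

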### **Time schedule of the project**

All the patients admitted to the Hospital starting from September 2009 for a first episode of myocardial infarction or unstable angina could be potentially involved in the study. The clinical picture will be evaluated by both means of ECG/echocardiogram charts and laboratory testing. At that time, cardiovascular risk factors, left ventricular ejection, HRV, TIMI and GRACE scores will be also provided. After one month of their admission, at their first control visit routinely scheduled by the cardiologists to check the clinical status of the patients, the clinical psychologists involved in the study will present to the patients the project to obtain informed consent. They will also administer interviews and questionnaires to select depressed patients. Among them, who were affected during the previous month by the presence of at least one of the following depressive emotional states such as DSM major or minor depression, dysthymia, DCPR demoralization, will be included in the study. The patients who will satisfy inclusion criteria will be randomized to one of the two treatments assignment. Both before and after the treatments, urinary and blood biomarkers of cardiac prognostic value will be detected. The duration of the study for each subject is expected to be 27-28 months. Included are 3-4 months of intervention and 24 months of follow-up. The duration of the overall study is expected to be 3 years for each patient. Every three months for the first year and then every 6 months for the following time, the patients will be reassessed through the same questionnaires by the same clinical psychologists who had evaluated them at the first assessment.

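### Does the cardiac-event survival analysis run on two conflicting clocks, one from baseline and one from the end of treatment?

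*Combined protocol and SAP*

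**What the plan says.** The third secondary endpoint, in the Endpoints paragraph under Specific aims and preliminary findings, is "the reduction of cardiovascular major adverse events (cardiac mortality, recurrent heart attack and new hospitalization for cardiovascular causes) after CBT-WBT versus CM".

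The STATISTICAL PLAN section gives its time origin: "Survival analysis will be used in order to evaluate the period of time occurred between baseline and new negative cardiac outcomes". The next sentence gives the length of follow-up: "The follow-up time considered for relapse will be 24 months after the end of the treatment". The sentence after that makes clear that relapse here means cardiac events, so both statements concern one endpoint. Kaplan-Meier curves, the log-rank test and a Cox model are named.

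Time schedule of the project states: "The duration of the study for each subject is expected to be 27-28 months". It breaks this down: "Included are 3-4 months of intervention and 24 months of follow-up". It then adds: "The duration of the overall study is expected to be 3 years for each patient".

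Study design and methods fixes the visits. For cardiology: "The cardiologists involved in the study will evaluate the patients at intake and once every 6 months". For the psychological scales: "Before and after psychological treatment, and then after 3, 6, 9, 12, 18 and 24 months". Both arms are planned as twelve weekly sessions, and randomisation follows the initial assessment.

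No section says outright whether events during treatment count, how event-free patients are censored, or when treatment ends for someone who stops attending.

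**The concern.** One endpoint is described with two reference dates, which allows two readings.

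- **Window opens at end of treatment.** The time schedule counts treatment and follow-up separately, and the endpoint is worded as a reduction after the interventions. An analyst could take 24 months from end of treatment as the whole window. Events in the first three to four months would be ignored, and the comparison would be restricted to patients event-free at the end of treatment instead of everyone randomised.
- **Window closes 24 months after treatment.** The clock starts at baseline, but the closing date depends on when treatment ended. That date falls after randomisation and can vary between patients.

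At stake is whether two analysts following the same text would report different event counts, and whether one of them would lose the randomised comparison. Treatment starts about a month after the index event, so the omitted months would be the earliest ones under observation. A further figure of 3 years per patient adds to the impression that the time frame is unsettled.

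**Working it through.** **1. Reproduce the plan's own figure.** Inputs from Time schedule of the project: treatment 3-4 months, follow-up 24 months.

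3 + 24 = 27 and 4 + 24 = 28, matching the stated 27-28 months. So origin at baseline and closure 24 months after treatment fit together. The 24-month psychological reassessment, counted from the post-treatment assessment, also falls at 27-28 months. Nothing in the components gives 36 months.

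**2. Person-time affected if the window opened at end of treatment.** 3/27 = 11.1%; 4/28 = 14.3%.

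**3. Events affected.** The documents give no cardiac event rate. Assume a constant hazard and a 24-month risk r of 10-40%, with treatment length L months. Per 100 patients:

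- during treatment: 100 × [1 − (1 − r)^(L/24)]
- whole period: 100 × [1 − (1 − r)^((24+L)/24)]

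| r | L | During treatment | Whole period | Share |
|---|---|---|---|---|
| 10% | 3 | 1.3 | 11.2 | 11.7% |
| 20% | 4 | 3.7 | 22.9 | 15.9% |
| 40% | 4 | 8.2 | 44.9 | 18.2% |

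**4. Hazard ratio.** Large-sample Cox limits with equal arms. All of the following are assumed: L of 3 or 4, control 24-month risk 10-40%, early hazard 1-3 times the later one, gamma frailty variance 0-2.

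| True effect | From randomisation | From end of treatment |
|---|---|---|
| HR 0.5 sustained | 0.50-0.62 | 0.50-0.69 |
| HR 0.5 during treatment only | 0.80-0.95 | 1.00-1.18 |

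With a sustained effect the largest difference between the two analyses is 0.065. At 20% risk, frailty variance 1 and a tripled early hazard they give 0.53 and 0.54.

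Hand check of one treatment-only case (r = 20%, L = 4, constant hazard, no frailty):

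- Early event probabilities: 0.0365 (control) and 0.0184 (treated).
- Late event probabilities: 0.9635 × 0.20 = 0.1927 and 0.9816 × 0.20 = 0.1963.
- Early share of events: 0.0549/0.4439 = 0.124.
- Approximate HR: exp(0.124 × ln 0.5) = 0.92, against 1.00 from end of treatment.
- With 50 per arm, about 50 × 0.4439 = 22 events are expected, so the standard error of the log HR is about 2/√22 = 0.43. Since ln 0.92 = −0.08, the effect is about a fifth of one standard error.

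**5. Variation in the closing date.** Suppose treatment is taken to end at the last attended session. A patient who leaves after two weeks closes at 0.5 + 24 = 24.5 months, and a four-month completer at 4 + 24 = 28 months, a spread of 3.5 months. If the scheduled end is used instead, twelve weekly sessions apply in both arms and the closing date is the same for everyone.

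**6. A single fixed cut-off.** Censoring everyone at 27 months would discard 28 − 27 = 1 month for a patient with four months of treatment. Six-monthly cardiology visits from intake fall at 24 and 30 months, so none coincides with it.

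**The case for a change.** The best case for a change is that the natural reading is not the only one. The follow-up sentence can be taken as a window opening at end of treatment, and no sentence rules that out. If the benefit were confined to the treatment months, that analysis would miss it (1.00-1.18 instead of 0.80-0.95). Even on the natural reading, the closing date hangs on a post-randomisation event that is undefined for early stoppers and might differ by arm. Non-cardiac death is not addressed either, although the endpoint counts cardiac mortality only.

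Some of this stands: these definitions are not written down. Three things limit its weight.

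- The first reading has to override an explicit statement that time runs from baseline. The endpoint's wording does not help it, because the primary score and the biomarkers are described in the same way; the wording names the comparison.
- Unequal follow-up lengths are ordinary in survival analysis and cause no bias when censoring is unrelated to prognosis. Both arms have the same planned session schedule, so a difference by arm is conjecture. A patient whose treatment is cut short by a cardiac event has already had the event, so the closing date does not matter for that patient. No bias has been shown.
- The treatment-only scenario runs against the plan's own expectation of lasting effects, and 100 patients could not tell those hazard ratios from 1.

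**Conclusion.** The concern does not call for a change. The plan states one origin, baseline, and a closing point that together reproduce its own 27-28 months. Followed that way, the analysis counts every event from baseline in all randomised patients, with largely administrative censoring that the named methods handle. An analyst would take baseline as intake or randomisation, which the plan places next to each other, and would censor at the planned close or last contact.

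The unnatural reading would remove 11-14% of person-time (from the documents) and 12-18% of events (assumed risks of 10-40%, constant hazard). It would shift a sustained hazard ratio of 0.5 by 0.00 to 0.07 under the assumed grid. No bias has been quantified for the natural reading. A fixed 27-month cut-off would bring no demonstrated gain, lose up to a month of planned follow-up, and match no cardiology visit.

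The 3-year figure is a clerical inconsistency in the time schedule, 8-9 months longer than the stated components, and the survival window does not rely on it. Only a secondary endpoint is involved.
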